6.2.3.2 Pulmonary Physiology, Exercise capacity, Gas Exchange

CCI

The same MMRM model described for the primary endpoint will be used in these analyses using SAS Proc Mixed.

Commercially Confidential Information

An ANCOVA

model will be fitted with treatment group as main factor, standard of care therapy (stratification factor) as a cofactor and baseline as covariate.

6.2.3.3 Model checking procedures

For the Time to Events Analyses, the assumption of proportional hazard will be visually assessed reviewing the Kaplan-Meier curves.

For the other analyses, the analyses of residuals will be performed to assess model assumptions.

6.2.3.4 Graphical presentation of results

6.2.3.4.1 Time to Events Analyses

Kaplan-Meier curves by treatment will be plotted.

6.2.3.4.2 Other analyses

Plots of mean values (with error bars representing SD) by treatment and visit will be released.

6.3 Exploratory objectives

Commercially Confidential Information

Commercially Confidential Information

6.3.2 Descriptive analyses

Commercially Confidential Information

Commercially Confidential Information

7 Statistical methods for safety and tolerability data

7.1 Variables

Adverse events, vital signs (blood pressure, pulse rate, body temperature), ECG intervals, laboratory measurements, as well as subject demographics, baseline characteristics, and treatment information.

7.2 Descriptive analyses

Subject demographics and other baseline characteristics

All data for background and demographic variables will be listed by treatment group and subject. Summary statistics will be provided by treatment group.

Commercially Confidential Information

Treatment

Data for study drug administration (rescue medication) and concomitant therapies will be listed by treatment group and subject.

Summary statistics will be provided for treatment compliance by treatment group.

The use of the standard of care medication (pirfenidone, nintedanib, or no treatment) will be summarized by treatment group.

Vital signs

All vital signs data (including pulse rate, systolic and diastolic blood pressure in sitting position, temperature and oxygen saturation) will be listed by treatment, subject, and visit and abnormalities as described below will be flagged.

Commercially Confidential Information

Table 7-1 Notable vital signs and body weight

Vital Sign Variable	Notable Criteria
---------------------	------------------

Pulse (beats/min)	>120 bpm or < 50 bpm
Systolic BP (mmHg)	≥ 160 mmHg or ≤ 90 mmHg
Diastolic BP (mmHg)	≥ 100 mmHg or ≤ 50 mmHg
Temperature (°C)	>38.3 °C/ 101°F
Body weight (kg)	More than 7% decrease from baseline weight

ECG evaluations

All ECG data (heart rate, QRS duration, RR, PR, QT and QTcF intervals) will be listed by treatment, subject and visit, and abnormalities as described below will be flagged. Summary statistics of value will be provided by treatment and visit. CCI

Table 7-2 ECG abnormalities

ECG abnormalities Variable	Notable Criteria
QT (ms)	Increase ≥ 30 ms
	Increase ≥ 60 ms
	New > 450 ms
	New > 480 ms
	New > 500 ms
QTcF (ms)	Increase ≥ 30 ms
	Increase ≥ 60 ms
	New > 450 ms
	New > 480 ms
	New > 500 ms
PR (ms)	increase > 25% or new > 200 ms
	New > 200 and ≤ 220 ms
	New > 220 ms
QRS (ms)	increase >25% or new > 110 ms
	New > 110 and ≤ 120 ms
	New > 120 ms
RR (ms) / HR (bpm)	RR increase > 25% or HR > 100 bpm
	RR decrease > 25% or HR < 60 bpm

Clinical laboratory evaluations

All laboratory data will be listed by treatment, subject, and visit and if normal ranges are available abnormalities will be flagged. Summary statistics will be provided by treatment and visit. Newly occurring liver enzyme abnormalities described in Table 7-3 will be summarized in treatment epoch. Newly occurring abnormality is defined when the abnormality occurs post baseline during the treatment epoch for patient without this abnormality at baseline .

Table 7-3 Liver enzyme abnormalities

Definition
ALT > 5x ULN

Definition
ALT > 10x ULN
ALT > 20x ULN
ALT or AST > 3x ULN
ALT or AST > 5x ULN
ALT or AST > 8x ULN
ALT or AST > 3x ULN & TBL > 1.5x ULN
ALT or AST > 3x ULN & TBL > 2x ULN
ALP > 1.5x ULN
ALP > 2x ULN
AST = Aspartate aminotransferase; also known as SGOT, ALT = Alanine aminotransferase; also known as SGPT, ALP = Alkaline phosphatase, TBL = Total bilirubin,

Listing and summary tables will be provided for the final analysis

CCI

Adverse events

All information obtained on adverse events will be displayed by treatment and subject.

Commercially Confidential Information

The number and percentage of subjects with adverse events occurring after the first dosing will be tabulated by body system and preferred term with a breakdown by treatment. A subject with multiple adverse events within a body system is only counted once towards the total of this body system and treatment. The same summary will be done for serious event.

The number and percentage of subjects with adverse events occurring after the first dosing by maximum severity of adverse events will be tabulated by body system and preferred term with a breakdown by treatment.

The number and percentage of subjects with adverse events occurring after the first dosing classified as related to study drug will be tabulated by body system and preferred term with a breakdown by treatment. The same summary will be done for serious event.

An overall summary of AEs will present incidence and occurrence of all AEs, AEs of mild intensity, AEs of moderate intensity, AEs of severe intensity, study drug-related AEs, serious AEs and AEs leading to discontinuation of study treatment.

If for a same patient, several consecutive AEs (irrespective of study treatment causality, seriousness and severity) occurred with the same SOC and PT:

- a single occurrence will be counted if there is \leq 1 day gap between the end date of the preceding AE and the start date of the consecutive AE
- more than one occurrence will be counted if there is $>$ 1 day gap between the end date of the preceding AE and the start date of the consecutive AE.

The number of deaths resulting from SAEs suspected to be related to study treatment and SAEs irrespective of study treatment relationship will be provided by SOC and PT.

Listing and summary tables, by epoch, will be provided for the final analysis

Commercially Confidential Information

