8.6.8 Electrocardiogram (ECG)

Full details of all procedures relating to the ECG collection and reporting are contained in the SOM.

ECG parameters will include: PR interval, QRS duration, heart rate, RR interval, QT interval, QTc. The Fridericia QT correction formula (QTcF) must be used for clinical decisions.

Clinically significant abnormalities must be reported in the AE CRF.

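### SAP Table 7-2: each RR/HR row joins a fast-rate and a slow-rate criterion, so the row flag alone does not give direction (minor; the two RR terms appear transposed)

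*SAP*

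**What the plan says.** SAP Section 7.2 (ECG evaluations) says that ECG abnormalities meeting the Table 7-2 criteria are flagged. The last variable in the table covers RR in ms and heart rate (HR) in bpm and has two rows:

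- Row 1: "RR increase > 25% or HR > 100 bpm"
- Row 2: "RR decrease > 25% or HR < 60 bpm"

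The PR and QRS rows of the same table also combine a percentage change with an absolute limit: "increase > 25% or new > 200 ms" for PR and "increase >25% or new > 110 ms" for QRS.

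The protocol (Sections 8.6.8 and 11.5.2) collects both heart rate and RR and says that abnormalities will be flagged, but gives no RR or HR limits. No visible text in either document explains the pairing in Table 7-2. Some text next to the table is redacted.

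**The concern.** RR and heart rate are reciprocal: when one goes up, the other goes down. Row 1 puts a lengthening of RR, which is a slowing, beside a limit for a fast rate. Row 2 puts a shortening of RR, which is a speeding up, beside a limit for a slow rate. In the PR and QRS rows both parts point the same way. Only the RR/HR rows do not, which suggests that the two RR terms were exchanged in drafting.

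The table acts as a programming specification. Coded literally, two categories that would be expected to separate fast from slow each contain both. A reader who sees only the row flag cannot tell whether the subject's rate was fast or slow. If row counts were tabulated by arm, those counts would mix the two.

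**Working it through.** **Inputs.** The two RR/HR criteria come from SAP Table 7-2. The only relation needed is RR (ms) = 60,000 / HR (bpm). The heart rates below are illustrative, not trial data. The documents state no figure on this point to reproduce.

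**Step 1: put the RR terms on the heart-rate scale.** With baseline rate b and follow-up rate h, the relative RR change is (60,000/h) / (60,000/b) − 1 = b/h − 1.

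- RR increase above 25%: b/h > 1.25, so h < 0.80b (slower).
- RR decrease above 25%: b/h < 0.75, so h > 1.333b (faster).

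As written, row 1 fires if h < 0.80b or h > 100, and row 2 fires if h > 1.333b or h < 60.

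**Step 2: apply the rows to examples.**

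| HR, baseline to follow-up | RR change, b/h − 1 | Rows fired as written | Row fired with RR terms exchanged |
|---|---|---|---|
| 95 to 72 | 95/72 − 1 = +31.9% | 1 only | slow |
| 90 to 105 | 90/105 − 1 = −14.3% | 1 only | fast |
| 62 to 90 | 62/90 − 1 = −31.1% | 2 only | fast |
| 65 to 58 | 65/58 − 1 = +12.1% | 2 only | slow |
| 80 to 58 | 80/58 − 1 = +37.9% | both | slow |
| 70 to 105 | 70/105 − 1 = −33.3% | both | fast |

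Each flag pattern (row 1 only, row 2 only, both) arises from a rise and from a fall.

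**Step 3: does knowing the baseline help?** Not reliably. At b = 85 the limits are 0.80 × 85 = 68 and 1.333 × 85 = 113.3. Row 1 alone then covers follow-up rates of 60 to below 68 and above 100 up to 113.3. Both rows together cover rates below 60 and above 113.3. Each pattern still spans slow and fast.

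**Step 4: check the logic over a range.** Take all integer pairs with baseline 60–100 and follow-up 35–140 bpm, which gives 41 × 106 = 4,346 pairs.

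| | As written | RR terms exchanged |
|---|---|---|
| Pairs with any flag | 3,100 | 3,100 |
| Row with HR > 100: rises / falls | 1,640 / 1,205 | 1,805 / 0 |
| Row with HR < 60: rises / falls | 1,380 / 1,025 | 0 / 1,295 |
| Pairs firing both rows | 2,150 | 0 |

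The totals reconcile: 1,640 + 1,205 + 1,380 + 1,025 − 2,150 = 3,100, and 1,805 + 1,295 = 3,100. The flagged set is identical because both versions use the same four conditions; only the sorting into rows changes. The grid weights all pairs equally and tests logic only. It does not predict trial counts.

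**The case against.** The strongest reply is that no visible output is shown to be wrong. The ECG listing carries the values themselves: "All ECG data (heart rate, QRS duration, RR, PR, QT and QTcF intervals) will be listed by treatment, subject and visit". Direction can therefore be read beside any flag. In addition:

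- "Summary statistics of value will be provided by treatment and visit", and SAP Section 7.3 adds boxplots of ECG data.
- Pulse has its own flag in Table 7-1 (">120 bpm or < 50 bpm").
- Protocol Section 8.6.8 requires that "Clinically significant abnormalities must be reported in the AE CRF", whatever Table 7-2 says.
- The SAP states that the Table 7-3 liver abnormalities will be summarised, but no such statement is visible for Table 7-2, so counts by row are an assumption.
- If RR and HR were flagged separately, each flag would show its own direction.
- Intent is unconfirmed. Both rows could come from grouping numerically high and numerically low values, or from copying the PR/QRS template without allowing for the reciprocal.

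All of this stands, and it limits the weight of the point. It does not make the rows coherent. A reader who can recover direction by hand from the listing is working around the specification. Whatever the cause, the rows as printed pair opposite directions, and nothing visible says that the two variables are flagged separately.

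**Conclusion.** The concern holds, as a minor drafting error in a descriptive safety table. That each row mixes directions follows from arithmetic and is certain. That the two RR terms were transposed is the likely explanation, but the documents do not confirm it. A PDF extraction fault is unlikely, because each criterion is one continuous line.

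The effect is confined to how RR/HR abnormalities are sorted. No record gains or loses a flag under re-pairing, and no endpoint, hypothesis test or analysis set is touched. A misleading result would require one flag per row shown without the values, or row counts by arm. Whether either is planned cannot be seen.

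**What to change.** Exchange the two RR terms in Table 7-2 and leave all four thresholds unchanged. The fast row then reads RR decrease above 25% or HR above 100 bpm; the slow row reads RR increase above 25% or HR below 60 bpm. The sponsor should confirm that this was the intent. If it was not, four separate flags, or a note that RR and HR are flagged individually, would also remove the ambiguity.

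After the exchange each row holds only fast or only slow criteria, and for baselines of 60 to 100 bpm each row also holds one direction of change. Exceptions remain outside that range, because the absolute limits ignore the baseline:

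- 110 to 102 bpm (110/102 − 1 = +7.8%) fires the fast row during a fall.
- 52 to 56 bpm (52/56 − 1 = −7.1%) fires the slow row during a rise.
- Both rows fire together only if 1.333b < h < 60, which needs b < 45, or 100 < h < 0.80b, which needs b > 125. An example is 40 to 58 bpm (40/58 − 1 = −31.0%).

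The cost is two table cells in the SAP and the matching program lines, before database lock. No new data are needed.

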5. Action taken regarding investigational treatment.

All adverse events must be treated appropriately. Treatment may include one or more of the following:

- no action taken (e.g. further observation only)
- investigational treatment dosage increased/reduced
- investigational treatment interrupted/withdrawn
- concomitant medication or non-drug therapy given
- hospitalization/prolonged hospitalization (see [Section 9.2](#) for definition of SAE)

6. its outcome (not recovered/not resolved; recovered/resolved; recovering/resolving, recovered/resolved with sequelae; fatal; or unknown).

Information about common side effects already known about the investigational drug can be found in the IB or will be communicated between IB updates in the form of Investigator Notifications (IN). Once an adverse event is detected, it must be followed until its resolution or until it is judged to be permanent, and assessment should be made at each visit (or more frequently, if necessary) of any changes in severity, the suspected relationship to the investigational drug, the interventions required to treat it, and the outcome.

The investigator must also instruct each subject to report any new adverse event (beyond the protocol observation period) that the subject, or the subject's personal physician, believes might reasonably be related to study treatment. This information must be recorded in the investigator's source documents; however, if the AE meets the criteria of an SAE, it must be reported to Novartis.

Refer to the SOM for data capture methodology regarding AE collection for subjects that fail screening.

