11.5.2 Safety

Vital signs

All vital signs data will be listed by treatment group, subject, and epoch/visit/time and if ranges are available abnormalities (and relevant orthostatic changes) will be flagged. Summary statistics will be provided by epoch, treatment and visit/time.

ECG evaluations

All ECG data will be listed by treatment group, subject and epoch/visit/time, abnormalities will be flagged. Summary statistics will be provided by epoch, treatment and visit/time.

Clinical laboratory evaluations

All laboratory data will be listed by treatment group, subject, and epoch/visit/time and if normal ranges are available abnormalities will be flagged. Summary statistics will be provided by epoch, treatment and visit/time.

Adverse events

All information obtained on adverse events will be displayed by treatment group, epoch and subject.

The number and percentage of subjects with treatment-emergent adverse events will be tabulated by body system and preferred term with a breakdown by treatment. A subject with multiple treatment-emergent adverse events within a body system is only counted once towards the total of this body system.

A treatment-emergent adverse event is defined as any adverse event that develops on or after the time of the first drug intake or any event already present that worsens following exposure to the study treatment.

All adverse events will be listed.

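### The readable SAP 7.2 counts adverse events after the first dose and does not carry over the worsening limb of the protocol's treatment-emergent definition

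*SAP*

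**What the plan says.** Protocol 11.5.2 plans the main AE table on treatment-emergent events: "The number and percentage of subjects with treatment-emergent adverse events will be tabulated by body system and preferred term". It defines such an event as one that "develops on or after the time of the first drug intake or any event already present that worsens following exposure to the study treatment". The definition therefore has two limbs, new onset and worsening.

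SAP 7.2 does not use the term in its readable text. Its main table reads: "The number and percentage of subjects with adverse events occurring after the first dosing will be tabulated by body system and preferred term". The severity table covers "adverse events occurring after the first dosing by maximum severity of adverse events will be tabulated", and the relatedness table covers "adverse events occurring after the first dosing classified as related to study drug will be tabulated". The serious-event versions are described as the same summaries.

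Two SAP outputs carry no first-dose limit in their wording. One is the display: "All information obtained on adverse events will be displayed by treatment and subject". The other is an overall summary of all AEs, split by intensity, relatedness, seriousness and discontinuation. The table of deaths states no such limit either.

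On collection, Protocol 9.1 counts AEs from written consent. It requires each event to be followed and reassessed at visits for "any changes in severity, the suspected relationship to the investigational drug" and other features. SAP 7.2 also has a merging rule: consecutive AEs in one patient with the same system organ class and preferred term, at most one day apart, count as one occurrence whatever their severity.

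**The concern.** SAP 1.1 presents the SAP as carrying out the analysis that the protocol plans, and the readable text announces no change to the AE definition. Yet the rule in SAP 7.2 is narrower than the protocol's. This is a conflict between two stated rules, not merely a missing detail.

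Adverse events are the first-listed secondary endpoint in both documents. Protocol 3.6 names upper respiratory tract infection and systemic injection reactions as identified risks. Protocol 7.5 warns that drug-related events can look like events of the underlying disease. Harm could therefore show as aggravation of a respiratory complaint that was already present, and that is what the worsening limb is there to catch.

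There is also a smaller timing gap. The protocol includes events at the time of first intake, whereas the SAP says after it. Protocol 6.9 reports first-dose reactions within 24 hours. If onset were compared by calendar date alone, which the documents do not specify, a literal reading could miss reactions on the day of dosing.

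**Working it through.** The plan states no figure for this point, so the check sets the two rules side by side for each type of event.

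| Event | Protocol 11.5.2 | SAP 7.2 tables limited to events after first dosing |
|---|---|---|
| (a) Onset after first dose | Counted | Counted |
| (b) Condition present before consent (medical history, Protocol 8.4) that worsens on treatment and is reported as an AE | Counted | Counted, because the AE starts after dosing |
| (c1) AE starting between consent and first dose, ongoing, worsens on treatment, worsening entered as a new record | Counted | Counted by subject; the merging rule could absorb it in occurrence counts |
| (c2) As (c1), but the worsening stays on the original record | Counted | Not counted, if occurring means onset |
| (d) AE starting before first dose that does not worsen | Not counted | Not counted |

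Only (c2) is lost from the subject-level tables, and only (c1) is exposed to the merging rule. The readable text of Protocol 9.1 requires changes in severity to be assessed, but does not say whether a worsening opens a new record. That unstated convention decides between (c1) and (c2).

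The overall summary does not restore the protocol's count. As worded, it would include (c2), but it would also include (d), which the protocol excludes. It has no stated breakdown by preferred term. The tables could then fail to reconcile with one another.

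For size, the documents allow only a bound on the pre-dose share of AE collection time. The inputs are a screening epoch of 6 weeks and a treatment epoch of 48 weeks (both SAP 1.4), and a two-year follow-up, taken as 104 weeks (Protocol 3.6.2).

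- Up to the end of treatment: 6 / (6 + 48) = 11.1%.
- Including follow-up: 6 / (6 + 48 + 104) = 3.8%.

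These shares assume a constant AE rate and full use of the 6-week screening. The events lost are this share multiplied by the fraction that are ongoing at first dose, worsen and stay on one record. The documents give no value for that fraction, so the product cannot be computed.

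**The case against.** The strongest reply is that the readable SAP may not be the whole rule. A redacted block stands directly before the quoted sentence in SAP 7.2, and there are others in the SAP's general definitions and after the AE text. A definition could stand there. This is why the point is limited to the readable text. It does not remove the point, because the readable sentences state their own restriction three times.

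A reader might infer that the SAP tabulates only post-dose events, or that pre-dose events that worsen disappear from the safety reporting. The documents do not support either. The overall summary covers all AEs, the deaths table has no stated first-dose limit, and all AE information is displayed by subject. A worsening entered as a new record has a post-dose start and is counted. The merging rule foresees back-to-back records of one event that may differ in severity, which fits that way of recording. The rule concerns occurrences, while the restricted tables count subjects.

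Eligibility also narrows the group. Exclusion 2 removes active infection needing systemic treatment at screening or enrollment, and exclusion 13 removes acute exacerbation or other significant clinical worsening within 3 months of randomization. Milder infections and cough remain possible.

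A reader might also put a figure on the loss by assuming that 5–20% of pre-dose AEs worsen. That gives 11.1% × 5–20% = 0.6–2.2% of all AEs up to the end of treatment, but 3.8% × 5–20% = 0.2–0.8% once follow-up is included. The 5–20% has no source in the documents, so neither range should be used as an estimate.

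**Conclusion.** The mismatch holds for the readable text. The tables by preferred term, maximum severity, relatedness and seriousness are limited to events after first dosing, and neither the worsening limb nor the on-or-after wording is carried over. The consequence is conditional. An AE that begins between consent and first dose and worsens on treatment is omitted from these tables only if occurring is read as onset and the worsening stays on the original record.

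The number of such events is probably small and cannot be derived from the documents. Nothing shows that a safety conclusion would change in this exploratory trial of about 58 subjects, which also has unblinded safety review by the data monitoring committee. This is a minor point, worth correcting because it is cheap and makes the tables for the first-listed secondary endpoint match the protocol. The verdict assumes that no redacted passage of the SAP already restores the definition.

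**What to change.** In SAP 7.2, define the treatment-emergent AE as the protocol does: onset on or after first drug intake, or already present and worsening after exposure. Then:

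- Use this definition in every AE summary table, including the serious-event tables and the overall summary.
- Count a worsened event at its maximum severity after the first dose.
- State whether a worsening is recorded as a new AE or as a severity change on the existing record, so that the flag can be programmed.
- State that the one-day merging rule does not fold a post-dose worsening record into an event that began before the first dose.

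If a redacted passage already contains this definition, a cross-reference from the table descriptions is enough. The cost is one definition and one programming flag. AE counts would rise slightly in both arms.
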